5.4. Visit 2: Randomization and Baseline Assessment

The following tasks will be performed and documented at the Visit 2 (Visit 2 could take place on the same day as Visit 1 and Visit 3) following informed consent:

- Reconfirm inclusion and exclusion criteria prior to randomization. Presence of AF in potential subjects who qualify for CRT-D implantation or existing CRT-D device will be confirmed as follows: AF present at screening visit and at 2 additional time points, one within 3 months and one ≥ 3 months prior to enrollment, with no intervening ECGs revealing sinus rhythm and/or no successful effort to restore sinus rhythm for > 24 hours.
- Subjects will undergo an echocardiogram at Baseline Visit prior to CRT-D implantation if no echocardiogram was performed within the past calendar year prior to randomization to qualify patient for CRT-D implant per current medical guidelines. For subjects with an existing CRT-D device, an echocardiogram demonstrating <15% change in LVSEV in comparison to pre-implant cardiac imaging must be within three calendar months prior to consent.

- Perform randomization to AVJ ablation or conventional treatment without ablation if potential subject meets as study eligibility criteria via the electronic data capture system or manually if internet access is not possible.

Note: Some of the following data will be required to confirm study eligibility criteria and recorded at time of screening confirmation and randomization. If not required to confirm study eligibility, this data will be recorded after randomization occurs.

- Perform clinical assessment and collect data on current prescribed CV medications
- Complete limited physical examination including vital signs, body weight, and height
- Perform symptom assessment
- Obtain a copy of standard 12-lead ECG used to confirm study eligibility
- Obtain most recent echocardiogram images obtained within 1 calendar year prior to or on randomization date used to determine study eligibility and prior to CRT-D implant
- Quality of Life assessment (prior to providing randomized treatment assignment to subject)

5.5. **Visit 3: Procedure Day(s)**

CRT-D implantation (unless subject has an existing, active CRT-D device) and AVJ ablation (in subjects randomized to AVJ ablation arm) are expected to be performed during this visit which must occur within on or within 1 calendar month after randomization date. These procedures could be performed on the same day as Baseline Visit 1 that will reflect usual clinical practice. Both procedures usually are performed on the same day while the subject is in electrophysiology lab for CRT-D implantation. However, the timing of the AVJ ablation is left to the discretion of physician. It is recommended that AVJ ablation be performed within 2 days of CRT-D implantation. Programming of CRT-D should need to be adjusted at the time of AVJ ablation as described above.

5.6. **Visit 4: Follow-up at 1 calendar month after Randomization** (1 calendar month \pm 7 days)

During this follow-up visit investigators/coordinators should:

- Perform limited clinical assessment, collect vital signs Obtain a copy of standard 12-lead ECG
- Assess CRT-D implant status
- Perform CRT-D interrogation and reprogramming as needed
- Obtain information regarding adverse events and congestive heart failure

5.7. **Visit 5: Follow-up at 3 calendar months after Randomization** (3 calendar months \pm 14 days)

During this follow-up visit investigators/coordinators should:

- Perform limited clinical assessment, collect vital signs and collect data on current prescribed CV medications
- Obtain a copy of standard 12-lead ECG
- Perform CRT-D interrogation and reprogramming as needed
- Obtain information regarding adverse events and congestive heart

5.8. **Visit 6: Follow-up at calendar 6 months after Randomization** (6 calendar months \pm 14 days)

During this follow-up visit investigators/coordinators should:

- Perform limited clinical assessment, collect vital signs and collect data on current prescribed CV medications
- Obtain a copy of standard 12-lead ECG
- Perform Echocardiogram per study echo acquisition manual
- Perform CRT-D interrogation and reprogramming as needed
- Obtain information regarding adverse events and congestive heart
- Quality of Life assessment
- Document closeout of subject participation in the study

5.9. Costs to the Subject

All treatments and tests are considered standard of care and as such will be billed using the patient's medical insurance coverage with the exception of the 6 month echocardiogram. There will be no charges for research activities to the subject. AVJ ablation is routinely performed in clinical practice and is routinely reimbursed. However, despite these practices there is no evidence from randomized clinical trials regarding clinical benefit of this procedure in those undergoing CRT-D implantation.

5.10. Payment for Participation

Subjects will not receive payment for participating in this research study.

5.11. Return of Individual Research Results

No research results will be provided to the subject other than the standard of care discussion of clinical outcomes.

5.12. Concomitant CV Medications

Optimal pharmacological treatment of heart failure is expected in enrolled subjects as defined by published guidelines from the American Heart Association and the American College of Cardiology.

5.13. Subject Withdrawals

Subjects will be advised in the written informed consent forms that they have the right to withdraw from the study at any time without prejudice. Subjects may be withdrawn as lost to follow-up by the investigator if they do not return for follow-up after 2 documented attempts to contact the subject. These subjects will not undergo any additional study activities prior to withdrawal.

6. ASSESSMENT OF STUDY ENDPOINTS

6.1. Echocardiogram (ECHO)

Echocardiographically quantified left ventricular systolic volume is the primary endpoint of this study. Subjects will undergo an ECHO at Baseline Visit prior to CRT-D implantation if no echocardiogram was performed within the past calendar year prior to randomization and at a 6-month follow-up visit after CRT-D implantation. The 6 month ECHO is expected to be paid for by the study and baseline echo is a standard-of care procedure normally performed before a CRT-D implantation. ECHO image acquisition performed after study consent must follow a standardized protocol; images will be digitized and sent to central ECHO Core Lab for blind assessment if possible. ECHO image acquisition that was performed to confirm eligibility prior to study consent will need to be sent to ECHO Core Lab at the Washington University in St. Louis for approval regarding correct images and quality after the subject signs the approved study consent. Sites will be supplied with training materials that will describe in detail the methodology for obtaining JAVA-CRT echocardiograms. Training sessions will be conducted and documented for all participating sites.

The ECHO will be sent to [name], Professor of Medicine/Cardiology at the Washington University in St. Louis Medical Center. [name] is respected leader in the field with vast experience as clinician and echocardiography expert. He has served as Director of ECHO Core Lab for numerous clinical trials including recent ECHO-CRT trial. He and his team will perform centralized blinded Echo reading. The ECHO will be used to also assess left ventricular diastolic volumes, left atrial volume, left ventricular function, and left ventricular dyssynchrony. We will request that echo data will be de-identified when sent from enrolling site to the ECHO Core Lab but just in case of identification still present the core lab will have "honest broker" who is a third party (an echo technician) who will receive the echos and de-identify them. The de-identified echos will then be analyzed by ECHO Core Lab.

6.2. Electrocardiogram (ECG)

Standard 12-lead ECGs are expected to be standard of care following CRT-D implant and/or AVJ ablation and will be obtained to document rhythm and presence of atrial fibrillation as well as to assess and document CRT-D paced QRS morphology.

6.3. CRT-D Interrogation

An interrogation of implanted CRT-D will be performed at each follow-up visit to document percentage of biventricular pacing and to document burden of appropriate and inappropriate ICD therapies. Assessment of CRT-D implant status and LV lead status will also be performed in addition to assessment of device programming.

6.4. Clinical Assessment

A clinical assessment will be performed to include functional status (NYHA class), interim hospitalizations, comorbidities, medications and heart failure event status. Vital signs and weight/height will be collected at baseline and at all study visits. Vital signs include blood pressure, and heart rate.

6.5. Quality of Life Assessment

Quality of life data will be acquired at baseline prior to the subject being informed of the randomized treatment assignment and at 6-month follow-up visit using the Kansas City Cardiomyopathy Questionnaire (KCCQ) administered to the subject.

6.6. Congestive Heart Failure

Subjects will be categorized as having a “heart failure event” when the subject has symptoms and/or signs consistent with heart failure and:

1. receives intravenous decongestive therapy (IV diuretics, IV nesiritide, IV inotropes), that does not involve formal in-patient hospital admission, regardless of the setting (i.e. in an emergency room setting, in the physician’s office, etc.), or
2. receives an augmented heart failure regimen with oral or intravenous medications during an in-hospital stay (formal hospital admission is defined as admission to hospital that includes a calendar date change).

Source documentation must be submitted to the CDC along with the completed CRF. Additional documentation will be requested from the enrolling center as needed. Initially, required documentation will only require a comprehensive discharge summary enabling the endpoint reviewer to determine the heart failure classification. If the discharge summary is not sufficient to determine a classification or additional information is needed to complete the heart failure adjudication data requirements then documentation will be requested from the enrolling center that may include some or all of the following, if available:

- History and physical, or admit note, or ER note
- Test results
- Chest X-ray, lab work, echo, ultrasound, other test results as appropriate
- Consults
- Operative reports
- Progress notes from the chart

The collection of heart failure events will stop at the point the trial is terminated, enrollment has been stopped, and the subject has had their last clinic follow-up visit.

7. SAFETY AND REPORTABLE EVENTS

7.1. Adverse Event Definition

An adverse event is any symptom, sign, illness, or experience that develops or worsens during the course of the study. Any adverse event related to the AVJ ablation should be reported regardless of whether it met the definition of a serious adverse event as described in Section 7.2. All serious cardiovascular adverse events

(including stroke) must be reported per definition in Section 7.2.

7.2. Serious Adverse Event Definition

A serious adverse event is defined as any adverse medical experience that results in any of the following outcomes:

- death;
- is life-threatening;
- requires inpatient hospitalization or prolongation of existing hospitalization;
- results in permanent impairment of a body structure or a body function;
- requires medical or surgical intervention to prevent permanent impairment or damage.
- lead to fetal distress, fetal death or a congenital abnormality or birth defect.

7.3. Recording Adverse Events Per Definition in Section 7.1

At each subject visit the site study staff will assess adverse events per definition in Section 7.1 by recording all voluntary complaints of the subject and by assessment of clinical and laboratory features. At each study visit, the subject should be questioned directly regarding the occurrence of any adverse experience since his/her last visit.

All adverse events, whether observed by the Investigator, elicited from or volunteered by the subject, should be documented on or following randomization date and within 10 calendar days of date reported to the enrolling site. Ventricular tachyarrhythmias will be documented in the ICD interrogations unless reported as an adverse event related to the AVJ ablation per the definition in Section 7.1. Each adverse event will include a brief description of the experience, the date reported to the enrolling site, the date of onset, the date of resolution, the duration and type of experience, the severity, relationship to subject condition, procedure, drug or device, contributing factors, and any action taken. Event status if not resolved will be tracked at each follow-up with final status indicated at the conclusion of study participation e.g., resolved, ongoing, unresolved.

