7.4. Responsibilities for Reporting Adverse Events

The Investigator will record all adverse events per Section 7.1 definition that occur during the study period in the appropriate source documents and/or AE case report form with 10 calendar days of the date reported to the enrolling site. The study period for reporting adverse events (e.g., from the time of randomization to final study visit) will be 6 months, the local IRB will be notified by the enrolling site per local IRB regulations. The Investigator will comply with local regulations regarding the reporting of adverse events. Adverse events reported by enrolling sites will be promptly reported to Data Coordinating Center Institutional Review Board, NIH, and FDA per local regulations. Similar to other clinical trials conducted by University of Rochester investigators, adverse events will be immediately reported to the Coordination and Data Center (CDC) via dedicated web-based case report forms to the PI ([name]) and Co-PI ([name]). The CDC will be forwarding relevant documents to the Chair of DSMB for review and Chair will determine whether individual case will require immediate assessment by full DSMB committee or it could be assessed during electively scheduled DSMB meeting. The main point of assessment by DSMB will be to judge whether given adverse event could be related to AV junctional ablation.

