8. RISK/BENEFIT ASSESSMENT

8.1. Potential Risks

Early risk to patients: The ablation catheter needs to be introduced through the femoral veins. This can result in either bleeding (hematoma) or thrombosis. The former was reported in 1 of 252 subjects (0.4%) in one study; the latter was reported in 1 of 156 subjects (0.6%) in another study. When the ablation is performed after implantation of the CRT device, it is possible to dislodge one of the implanted leads with the ablation catheter;

this was observed in 2 of 156 subjects (1.2%) in a prior study. This complication would require repositioning of the lead(s) that dislodged.

Late complications: There are 2 feared late complications of AV junction ablation. The first is that dislodgement of the ventricular lead in a pacemaker dependent subject could be fatal. However, a stable underlying escape rhythm is present in 67% of subjects following ablation. In addition, each subject in this trial will be undergoing biventricular pacing. It would be distinctly unusual for both the right and left ventricular leads to dislodge at the same time. Dislodgement of one ventricular lead would lead to loss of biventricular pacing but would still allow the other ventricular lead to pace the heart. In addition, contemporary left ventricular leads are multipolar, providing additional pacing redundancy.

The second feared complication is polymorphic ventricular tachycardia. In early trials of AV junction ablation, sudden cardiac death was observed in ~5% of patients. It was subsequently recognized that this was due to bradycardia-dependent polymorphic tachycardia. This adverse event can be eliminated by gradually reducing the lower pacing rate after initial programming is set at a higher than usual lower rate cutoff (as has been designed in this trial). Arrhythmic mortality was observed in only 2 of 252 subjects (0.8%) when such a protocol was routinely employed in a post-AV junction trial of pacemaker patients. In our study, all subjects will have an implantable defibrillator; thus, in the extremely rare event that a subject develops post-ablation polymorphic ventricular tachycardia, the defibrillator would be able to resuscitate the subject.

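### Section 7.3 conflicts with 7.1 and 7.2: a serious ventricular tachyarrhythmia that the site considers unrelated to ablation may never become an adverse-event report

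*Combined protocol and SAP*

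**What the plan says.** Section 7.1 sets two reporting rules. The first turns on cause: "Any adverse event related to the AVJ ablation should be reported regardless of whether it met the definition of a serious adverse event". The second turns on seriousness: "All serious cardiovascular adverse events", stroke included, "must be reported per definition in Section 7.2". The second carries no condition about cause. Section 7.2 lists the outcomes that make an event serious. One is that the event "is life-threatening"; death and inpatient hospitalization are others. Arrhythmia is not excepted.

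Section 7.3, on recording, adds: "Ventricular tachyarrhythmias will be documented in the ICD interrogations unless reported as an adverse event related to the AVJ ablation". It refers back to the definition in 7.1 for that exception and states no other.

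Section 7.4 describes what follows an adverse-event report. The site records the event within 10 calendar days of its being reported to the site. The coordination and data center (CDC) receives it and forwards the relevant documents to the DSMB chair, who decides whether the full board should look at once or at a scheduled meeting. It then says: "The main point of assessment by DSMB will be to judge whether given adverse event could be related to AV junctional ablation".

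Section 8.1 describes two feared late complications of ablation: "The second feared complication is polymorphic ventricular tachycardia". Section 6.3 gives the source of the device data: "An interrogation of implanted CRT-D will be performed at each follow-up visit". Section 9 says that data on ventricular tachyarrhythmias needing ICD therapy, and on deaths, will go to the DSMB.

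**The concern.** Sections 7.1 and 7.3 give a site different instructions for the same event. Take a life-threatening VF episode that the site puts down to the underlying cardiomyopathy. Under 7.1 and 7.2 it must be reported. Under 7.3, read as written, it goes into the device record and no adverse-event form is called for.

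This matters because the only route to prompt review of an individual case starts from an adverse-event report. If 7.3 is followed, the opinion of an unblinded site decides whether the chair sees the case, before the board has made the judgement that 7.4 assigns to it. The event type concerned includes one that the protocol itself names as a feared consequence of the procedure under test.

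**Working it through.** The plan states no figure on this point, so the check is a comparison of the rules. A ventricular tachyarrhythmia can be serious or not under 7.2, and attributed or not attributed to ablation by the site. That gives four classes.

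| Class of event | 7.1 with 7.2 | 7.3 as written | Agree? |
|---|---|---|---|
| Serious, attributed | Report | Report | Yes |
| Not serious, attributed | Report | Report | Yes |
| Serious, not attributed | Report | Device record | **No** |
| Not serious, not attributed | No report required | Device record | Yes |

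Three classes agree and one does not. Section 7.3 keeps the first rule of 7.1 (relatedness) and leaves out the second (seriousness).

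Next, what happens to the third class if a site follows 7.3:

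1. **Route in 7.4.** It begins with an adverse-event report. Without one there is no form to the CDC and nothing for the chair to triage.
2. **Section 9.** The board still receives ICD-treated arrhythmias as collected study data. No interval is given for supplying them, and meetings are keyed to groups of 20 enrolled subjects, not to events.
3. **Any parallel process.** Heart failure events have one: Section 13 provides source documents, committee adjudication and a confirmation document sent to the DSMB. The protocol describes nothing similar for ventricular tachyarrhythmias. The ablation safety endpoints in Section 11 include cardiac arrest during the procedure, but no later ventricular arrhythmia.

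So the loss for this class is case-level, prompt triage. Aggregate visibility remains.

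On size, Section 8.1 gives arrhythmic mortality of 2 in 252 under a pacing-rate protocol (2/252 = 0.79%, agreeing with the stated 0.8%) and sudden death of about 5% in early trials. Both are rates of death. The protocol gives no rate for non-fatal serious VT or VF and no rate at which sites would call such events unrelated. The number of reports at stake therefore cannot be calculated from the documents.

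**The case against.** The best reply is that 7.3 only names a data source. It says where ventricular tachyarrhythmias are documented; it does not say that serious ones go unreported. The requirement in 7.1 is mandatory, 7.4 has the investigator record all events that meet the 7.1 definition, and Section 12 makes the investigator responsible for reporting every event within the protocol definition. On that reading 7.1 governs and nothing is lost. This is a reasonable reading, and many sites may adopt it. But 7.3 does state an exception, and having stated one it gives only relatedness. Sites could follow either section in good faith.

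It is also fair to say that site attribution is not peculiar to 7.3. Section 7.1 uses it for non-serious events, and Section 12 asks investigators to assess relationship. That stands. The difficulty arises only where attribution overrides the seriousness rule.

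A reader might infer more than the documents support:

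- **That the DSMB would not see VT/VF at all.** Section 9 provides ICD-treated episodes.
- **That 7.3 delays detection by the months between visits.** The 10-day clock runs from report to the site, and adverse events are elicited at the same visits, so an episode the subject did not notice surfaces at interrogation under either rule. Table 1 also lists episode reports at the procedure visit, and nothing forbids an unscheduled interrogation.
- **That the death rates in 8.1 measure the reports lost.** Death is serious in its own right under 7.2, and death data go to the board in any case.
- **That the comparison of arms is biased.** The planned comparison of appropriate ICD therapy, secondary endpoint (e), uses device data from both arms, whatever the site's opinion.
- **That every shock or syncope is serious.** Section 7.2 lists neither.

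**Conclusion.** The conflict is real and narrow. For ventricular tachyarrhythmias that are serious under 7.2 and not attributed to ablation by the site, 7.1 requires a report and 7.3 as written does not. If 7.3 is followed, the case bypasses the chair's triage in 7.4, and the board meets it later among collected data, with no stated timeline.

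This rests on two assumptions: that at least some sites would take the exception in 7.3 at its word, and that some such episodes would meet 7.2, most plausibly as life-threatening. Neither can be quantified from the documents. The primary endpoint, the power calculation and the planned between-arm analysis of ICD therapy are not affected. The weakness lies in safety monitoring, and it should be corrected because it concerns a complication that the protocol itself singles out.

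**What to change.** Reconcile 7.3 with 7.1, 7.2, 7.4 and Section 9 by adding to 7.3, in substance:

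> Documentation in the device record alone does not apply to any ventricular tachyarrhythmia that is serious under Section 7.2. Such events are reported in both arms through Section 7.4, regardless of the site's view of relatedness, with the available device episode report attached. Non-serious episodes not attributed to ablation remain in the interrogation record.

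This leaves the definition of seriousness in 7.2 as it stands and lets the DSMB make the relatedness judgement that 7.4 gives it. A cross-reference in Section 9 would make clear that these case reports are separate from the arrhythmia data already supplied to the board.

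The cost is a one-paragraph amendment and a few more adverse-event forms across 40 subjects, using device reports that sites already obtain. It adds no procedure or visit and does not alter clinical management.
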